# Introduction

Psoriasis is a chronic, incurable skin disease affecting millions of people worldwide. Nail abnormalities occur concomitantly in 50% of patients with psoriasis, with a lifetime incidence of 80% to 90%.(1) In patients with psoriatic arthritis the incidence of nail disease is greater than 80%.(2) Nail psoriasis significantly impacts quality of life. In a survey of 1728 patients, 93% considered it a significant cosmetic handicap, 52% reported pain as a symptom and 58% reported difficulty carrying out their job.(3) Treatment of nail bed psoriasis poses a challenge to the clinician as there is a lack of controlled clinical trials and no gold standard for therapy to date. When nail bed psoriasis is not associated with widespread skin disease or psoriatic arthritis, topical treatment should be the initial approach. The choice of treatment depends on the type of disease present. Many physicians use topical and intralesional corticosteroids or a vitamin D analog for treatment of nail bed disease (eg onycholysis and subungual hyperkeratosis) (4). There are published reports demonstrating the increased tolerability of calcitriol ointment as compared to calciprotriol cream in the treatment of the sensitive intertriginous areas (5, 6)

In a study by Tosti et al. calcipotriol was as effective as a corticosteroid preparation at reducing subungual hyperkeratosis. (7) Adverse events with vitamin D analog therapy were limited to erythema and burning irritation. The nail unit is a sensitive area that might benefit from a less irritating vitamin D topical medication. In a pilot study by Kole, Cantrell, and Elewski, it was demonstrated that calcitriol ointment was as effective as betamethasone diproprionate ointment for the treatment of nail thickness in nail psoriasis. (8) Furthermore, in a study by Park et al. the fixed combination formulation of calcipotriol/betamethasone diproprionate ointment was safe and effective in the treatment of trachyonychia, which may be associated with psoriasis. (9) Lind et al demonstrated that the fixed combination calcipotriene/betamethasone diproprionate foam had greater skin penetration than the ointment formulation. (10) As such we propose that the combination product of vitamin D and topical steroids in the foam formulation (specifically, Cal/BD Foam), with increased penetration, will be an effective and safe option in the topical treatment of nail psoriasis.

The aim of the proposed study is to evaluate the efficacy and safety of Enstilar Foam (calcipotriene and betamethasone dipropionate) for the treatment of nail psoriasis.

# STUDY OBJECTIVES

# **Primary Objective**

To compare the efficacy of a 24-week regimen of twice daily Enstilar Foam (calcipotriene and betamethasone dipropionate) in the treatment of nail bed psoriasis. The primary efficacy outcome measure is the proportion of subjects achieving clinical improvement as measured by the nail thickness (hyperkeratosis) measurement.

# Secondary Objectives

- 1. modified NAPSI (mNAPSI) score of target nail at Baseline, wk 12 and wk 24
- 2. NAPSI score of target nail at Baseline, wk 12 and wk 24
- 3. Physician global assessment (PGA) of nail disease.
- 4. Determine the most optimal method of assessing nail psoriasis (mNAPSI or NAPSI).

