### STUDY DESIGN

### **Study Outline**

This is open label investigator initiated study to examine the efficacy and safety of twice daily Enstilar Foam (calcipotriene and betamethasone dipropionate) in a population of nail bed psoriasis subjects who are eligible for topical treatment as deemed by the investigator.

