### Number of Subjects

Up to 20 eligible subjects will be provided twice daily daily Enstilar Foam (calcipotriene and betamethasone dipropionate). Subjects will be instructed to apply a thin layer on the nail plate, around the nail plate and under the nail plate. The patient will be instructed to apply one application at night immediately before bed and not wash their hands before morning. At week 12, those patients with a mNAPSI50 or less may elect to discontinue study treatment. All subjects who completed the 6-month treatment will be followed for 1 month after discontinuation.

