### Study Visit

Subjects will report monthly to the investigational site for nail assessments.

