# STUDY FLOWCHART:

Vectical vs. Betamethasone	Screening	Treatment						Follow Up	
	Within 28	Visit 1	2	3	4	5	6	7	8
	Days Prior	W k 1	Wk 4	Wk 8	Wk 12	Wk 16	Wk 20	Wk 24	Wk 28
Test / Evaluation	to Day 1	Day 1	22	50	78	106	134	162	
Informed Consent	х								
Medical History	х								
Physical Exam	Х						х		
Psoriasis Nail Assessment (mNapsi, NAPSI)	х	х	x	х	х	х	х	х	Х
Nail Thickness Measurement	х	х	х	х	х	х	х	х	Х

Vital Signs	х	х	х	х	x	x	х	х	Х
Urine Pregnancy Test 		х						х	
Photography		х	х	х	х	х	х	х	Х
Adverse Events		х	x	х	x	х	х	x	Х
Concomitant Medications	х	x	x	х	x	x	х	x	Х

References:

- 2. Lawry M. Biological therapy and nail psoriasis. Dermatol Ther.20(1):60-7.
- de Jong E, Seegers B, Gulinck M, Boezeman J, van de Kerkhof P. Psoriasis of the nails associated with disability in a large number of patients: results of a recent interview with 1,728 patients. Dermatology. 1996;193(4):300-3.
- 6. Wozel, G. Psoriasis treatment in difficult locations: scalp, nails, and intertriginous areas. Clinics in Dermatology. 2008; 26: 448-59.

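### No visit-masked reading is specified for mNAPSI and NAPSI in this single-arm open-label study, although photographs with no stated use are already scheduled at the three time points those objectives name

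*Protocol*

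**What the plan says.** - **Design.** Protocol, Study Outline: "This is open label investigator initiated study to examine the efficacy and safety of twice daily Enstilar Foam". Number of Subjects: "Up to 20 eligible subjects will be provided twice daily" foam. One regimen is described and there is no control arm.
- **Scores.** Protocol, Secondary Objectives, items 1 and 2: "modified NAPSI (mNAPSI) score of target nail at Baseline, wk 12 and wk 24" and "NAPSI score of target nail at Baseline, wk 12 and wk 24". Item 3 is "Physician global assessment (PGA) of nail disease", with no time point. Item 4 sets out to decide which of mNAPSI and NAPSI is the better instrument.
- **Where scoring happens.** Protocol, Study Visit: "Subjects will report monthly to the investigational site for nail assessments". The protocol does not say who scores or what the scorer knows, and it names no masked, independent or second reading.
- **Photographs.** In the Study Flowchart, Photography is marked at Day 1 and Wk 4, 8, 12, 16, 20, 24 and 28. That row is the only mention of photography in the protocol. It does not say which nails are photographed or what the pictures are for.
- **Primary outcome.** Protocol, Primary Objective: "the proportion of subjects achieving clinical improvement as measured by the nail thickness (hyperkeratosis) measurement". This is a measurement, not a graded score.

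**The concern.** In a single-arm study there is no allocation to hide, but it is still possible to hide whether a nail is being seen before or after treatment. The protocol leaves that open for its two graded nail scores. A rater who expects improvement after 12 or 24 weeks of active treatment may score lower without meaning to. With no concurrent control, that shift goes straight into the change from baseline.

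The scores also matter beyond description. The option to stop treatment at week 12 refers to mNAPSI, and the fourth secondary objective compares mNAPSI with NAPSI as instruments. If one scale yields more readily to expectation than the other, it could look the more responsive of the two for that reason alone.

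What makes this worth raising in a small open-label study is that the material for a masked reading is already being collected.

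**Working it through.** **Step 1: compare the flowchart rows.** Inputs: the row that begins "Psoriasis Nail Assessment (mNapsi, NAPSI" and the Photography row.

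| | Screening | Day 1 | Wk 4 | Wk 8 | Wk 12 | Wk 16 | Wk 20 | Wk 24 | Wk 28 |
|---|---|---|---|---|---|---|---|---|---|
| mNAPSI, NAPSI | x | x | x | x | x | x | x | x | x |
| Photography | – | x | x | x | x | x | x | x | x |

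The scores have 9 marks and photography has 8; only Screening is scored without a picture. If Day 1 is taken as Baseline, photographs exist at all three time points in items 1 and 2 of the Secondary Objectives. PGA has no flowchart row and no time point, so its visits cannot be matched to photographs.

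**Step 2: look for any masked reading or any use of the photographs.** There is none in the objectives, the study design, the procedures or the safety plan.

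**Step 3: illustrate the size.** The protocol gives no SD, drift, test or power calculation for these scores, so there is no stated figure to reproduce. Every input below except n is an assumption:

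- n = 20, the ceiling in Number of Subjects;
- percent improvement in score roughly normal, with SD s of 20 to 50 points;
- true mean improvement zero, and rater drift d in favour of treatment;
- a two-sided 5% paired t-test.

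The test statistic follows a noncentral t distribution with n − 1 = 19 degrees of freedom and noncentrality d / (s/√n). The critical value is t(0.975, 19) = 2.093. For d = 10:

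| SD s | s/√20 | Noncentrality | P(significant in favour of treatment) |
|---|---|---|---|
| 20 | 4.472 | 2.236 | 0.5645 |
| 30 | 6.708 | 1.491 | 0.2932 |
| 40 | 8.944 | 1.118 | 0.1847 |
| 50 | 11.180 | 0.894 | 0.1335 |

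Without drift the figure is 0.025.

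Varying the drift at s = 30: d = 5 gives 0.1054, d = 10 gives 0.2932 and d = 15 gives 0.5645.

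With n = 10 and d = 10 (9 degrees of freedom, critical value 2.262), SDs of 20, 30, 40 and 50 give 0.2928, 0.1551, 0.1056 and 0.0820. For a fixed drift the rate rises with n, so recruiting more subjects does not cure the problem.

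**The case against.** **The protocol makes no error here.** It openly declares an open-label design, claims no masking anywhere and contradicts itself nowhere on the point. Assessor arrangements could be written in a document not shown. This stands in part: it makes the point an improvement and not the correction of a mistake. Still, how outcomes are assessed is a procedure that belongs in a protocol, and this protocol schedules photographs without giving them a purpose.

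**Stronger readings are tempting, and the documents do not support them.**

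- A reader might infer that every efficacy outcome is affected. The primary outcome is a nail thickness measurement. Its device and assessor are not described, and re-reading photographs would not test it.
- A reader might infer that every scored visit has a photograph. Screening does not.
- A reader might include PGA. No PGA visit is scheduled, so neither its timing nor its photographic cover can be checked.
- A reader might take it as stated that the assessor knows the visit. That is inferred from open-label scoring at site visits; nothing in the protocol says so, and nothing prevents it.

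**The size is assumed.** This stands in full. Drift, SD and test are all supplied from outside the protocol, and 20 is a maximum.

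**The remedy is imperfect.** An assessor who has seen at most 20 subjects repeatedly may recognise some nails. Some nail bed signs may show poorly in a picture, and the flowchart does not say that the target nail is photographed. These limits stand. They are reasons to keep the live scores and not to let photographs overrule them. They are not reasons to leave the photographs unused.

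**Conclusion.** The point holds for mNAPSI and NAPSI. As written, the protocol offers no check on rater expectation for these two scores, although photographs fall on all three of their named time points, with Day 1 taken as Baseline.

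The numbers show how a drift would act, not that one will occur. Under the assumptions above, with 20 subjects, a 10-point drift and no true effect, the chance of a nominally significant benefit is about 13% to 56% as the SD falls from 50 to 20 points, against 2.5% without drift.

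This is a cheap improvement to secondary outcomes. It does not show that the primary result is biased. Nor would masked reading turn the before-after change into a treatment effect: regression to the mean and the natural course of the disease would remain in it.

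**What to change.** Add to the study procedures:

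1. State that the target nail is included in the scheduled photographs, and that Day 1 is the baseline for this comparison.
2. After the last visit, strip the Day 1, Wk 12 and Wk 24 images of subject and date labels and shuffle them. The existing assessor then scores them for NAPSI and mNAPSI without knowing the visit.
3. Report the masked change beside the live change as a sensitivity analysis, together with the agreement between the two readings.
4. If the two differ on a score, qualify any efficacy conclusion drawn from that score. The photographs do not veto the live scores.
5. Add PGA to the masked reading only once its visits have been scheduled.

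**Cost.** A short protocol addition and a few hours of the assessor's time for at most 20 × 3 = 60 sets of photographs. No new reader, visit or procedure is needed. The downsides are that some signs show less well on photographs and that the assessor may recognise some nails. Both should be acknowledged when the results are reported.

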### Additional Objectives

To assess the safety of a 24-week regimen of twice daily Enstilar Foam (calcipotriene and betamethasone dipropionate) in the treatment of nail bed psoriasis.

### STUDY DESIGN

### **Study Outline**

This is open label investigator initiated study to examine the efficacy and safety of twice daily Enstilar Foam (calcipotriene and betamethasone dipropionate) in a population of nail bed psoriasis subjects who are eligible for topical treatment as deemed by the investigator.

### Number of Subjects

Up to 20 eligible subjects will be provided twice daily daily Enstilar Foam (calcipotriene and betamethasone dipropionate). Subjects will be instructed to apply a thin layer on the nail plate, around the nail plate and under the nail plate. The patient will be instructed to apply one application at night immediately before bed and not wash their hands before morning. At week 12, those patients with a mNAPSI50 or less may elect to discontinue study treatment. All subjects who completed the 6-month treatment will be followed for 1 month after discontinuation.

### Visit Schedule

### Screening Period

Patient eligibility will be determined within 28 days prior to study entry. Subjects who meet the entry criteria may proceed to the first dosing visit.

### **Dosing Visit**

Subjects will report to the investigational site to receive twice daily Enstilar Foam (calcipotriene and betamethasone dipropionate)

### Study Visit

Subjects will report monthly to the investigational site for nail assessments.

### Follow-Up Visits

Subjects will return to the investigational site for follow-up visit at 4 weeks after the last study visit.

### **Discontinuation of the Study**

The study may be discontinued at the discretion of the investigator at any time.

# STUDY ENTRY CRITERIA

### Study Inclusion Criteria

To be eligible to participate in this study, candidates will meet the following eligibility criteria at the time of enrollment:

- 1. Give written informed consent prior to any study procedures being conducted, and candidates will authorize the release and use of protected health information (PHI)
- 2. Between the ages of 18 and 85 years old
- 3. Have a diagnosis of nail psoriasis in either fingernails or toenails.
- 4. Candidate for topical therapy in the opinion of the investigator.
- 5. History of plaque psoriasis or psoriatic arthritis
- 6. Target nail will be KOH negative for dermatophyte fungus

# Study Exclusion Criteria

Candidates will be excluded from study entry if any of the following exclusion criteria exist at the time of enrollment:

- 1. Males and females unable to practice effective contraception throughout study treatment
- 2. Unable to comply with the protocol (as defined by the Investigator; i.e. drug or alcohol abuse or history of noncompliance)
- 3. The presence of skin or nail conditions that might interfere with patient status assessments, as determined by the study investigator.
- 4. Nursing mothers, pregnant women, and women planning to become pregnant while in this study.
- 5. Patients with erythrodermic or pustular psoriasis.
- 6. Other sustained treatment to target fingernail within 6 months prior to screening.
- 7. History of trauma or surgery to target fingernail.
- 8. History of any disease known to affect nails (e.g., lichen planus, onychomycosis)
- 9. History of systemic psoriasis therapy for less than 6 months

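### The prior-treatment and trauma/surgery exclusions reach only a target fingernail, although toenail psoriasis qualifies and the target nail is not defined

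*Protocol*

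**What the plan says.** Protocol, Study Inclusion Criteria:

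- Item 3: "Have a diagnosis of nail psoriasis in either fingernails or toenails". This concerns the diagnosis and does not say which nail is to be followed.
- Item 6: "Target nail will be KOH negative for dermatophyte fungus". No site is given.

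Protocol, Study Exclusion Criteria:

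- Item 6: "Other sustained treatment to target fingernail within 6 months prior to screening".
- Item 7: "History of trauma or surgery to target fingernail".
- Item 3, at the investigator's discretion: "The presence of skin or nail conditions that might interfere with patient status assessments, as determined by the study investigator".

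Secondary Objectives ties two measures to the target nail, again without a site. One is the "NAPSI score of target nail at Baseline, wk 12 and wk 24", and the mNAPSI item matches it. The Primary Objective names nail thickness but does not say on which nail it is measured, and neither does the flowchart.

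The only other hint about site is the application instruction under Number of Subjects: "The patient will be instructed to apply one application at night immediately before bed and not wash their hands before morning". The protocol text available does not define the target nail or say how it is chosen.

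**The concern.** Exclusions 6 and 7 keep out nails whose condition at entry may reflect something other than untreated psoriasis. The protocol applies them to a fingernail and gives no reason for treating a toenail differently, yet toenail disease is enough to qualify. An investigator with a toenail candidate cannot tell from the text whether that toenail may be the target or, if it may, whether its treatment and injury history matters.

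This matters more here than in a controlled trial. With no comparison arm described, change can be judged only against the subject's own starting value. A nail still responding to an earlier treatment, or altered by injury or surgery, starts from a disturbed value, and no control group would show it.

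**Working it through.** The protocol states no figure on this point, so the check is a comparison of the entry rules.

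**Step 1. Each rule applied to the two kinds of target nail.**

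| Protocol rule | Target is a fingernail | Target is a toenail |
|---|---|---|
| Inclusion 3, qualifying disease | met | met |
| Inclusion 6, negative fungal test | applies | applies |
| Exclusion 6, other sustained treatment in the 6 months before screening | applies | not written |
| Exclusion 7, trauma or surgery | applies | not written |
| Exclusion 3, interfering conditions | discretionary | discretionary |
| Exclusion 8, other nail disease | applies | applies |

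The wording count agrees. Target nail appears 3 times (both NAPSI objectives and inclusion 6), target fingernail twice (exclusions 6 and 7), toenails once (inclusion 3), and a definition of the target nail not at all in the text available.

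**Step 2. Two candidates alike except for site.** Each has had sustained local treatment of the target nail in the months just before screening. The fingernail candidate is excluded by item 6. The toenail candidate passes every written rule. With past trauma or surgery instead, item 7 excludes the first and again does not reach the second.

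**Step 3. Whether another rule closes the gap.**

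- Exclusion 8 concerns diseases of the nail, not its treatment or injury.
- Exclusion 9 and the section on concomitant psoriasis therapy concern systemic treatment.
- General Concomitant Therapy asks for an effort to hold prescription medication at a stable dose for 14 days before the first dose. A stable dose is not absence of treatment.
- Exclusion 3 could be used for a visibly damaged toenail. It depends on judgement and on a condition being present, so recent treatment does not in itself meet its wording.

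Earlier local treatment of a target toenail is left uncovered. Trauma and surgery are covered only by discretion.

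**Step 4. The alternative, that only a fingernail can be the target.** Exclusions 6 and 7 then cover every target nail. Inclusion 3 becomes too wide, because it lets in a toenail-only diagnosis while inclusion 6 presupposes a target nail that such a candidate does not clearly have.

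**Step 5. Which outcomes are touched.** mNAPSI and NAPSI are scored on the target nail, so the link is explicit. For nail thickness it is conditional on thickness being measured on the same nail.

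**Step 6. Scale.** If all 20 subjects are enrolled and analysed, one subject is 1/20 = 5 percentage points of the primary proportion, and more if fewer are analysed. This shows how much one subject weighs and is not an estimate of bias. An estimate would need the share of target toenails, the frequency of such histories and their effect on the measurements. The protocol gives none of these.

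**The case against.** The strongest reply is that this is loose wording with little behind it. The hands-only instruction may suggest that fingernails were meant throughout. Exclusions 3, 8 and 9 already remove interfering nail conditions, nail disease and recently started systemic therapy at any site. The study is small, and nobody can say how many subjects would be affected. Much of this stands: what remains uncovered is mainly earlier local treatment of a target toenail, and no effect on the result has been shown. But the hands instruction does not define the target nail, and a discretionary rule does not replace two specific ones.

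Three stronger readings are tempting, and the protocol does not support them.

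- A reader might infer a 6-month treatment-free period for fingernails against none for toenails. Exclusion 6 bars only other sustained treatment, and stable systemic therapy is allowed. Even a target fingernail need not be untreated. The contrast is that a bar on other sustained treatment is written for one site and not for the other.
- A reader might infer that the primary endpoint is compromised. The Primary Objective does not tie thickness to the target nail, so that step is an assumption.
- A reader might infer that, if only fingernails can be targets, toenail-only subjects would be enrolled with nothing to assess. Such a candidate cannot clearly meet inclusion 6, so enrolment does not follow. What follows is that inclusion 3 is too wide.

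**Conclusion.** The entry criteria are inconsistent on site and should be corrected. If a toenail may be the target, two baseline-protecting exclusions do not reach it. If only a fingernail may be, inclusion 3 admits more than the other criteria can accommodate. The text does not show which was intended.

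For the rules, the size is definite: two exclusions written for one site and not the other. For the results it is unknown in amount and direction, since earlier treatment, injury or surgery could move a baseline either way. The risk to mNAPSI and NAPSI rests on a toenail being accepted as the target. The risk to nail thickness rests also on its being measured on that nail. This is a correction to make in the protocol, because an analysis plan cannot repair eligibility afterwards. It is not a demonstrated threat to the result.

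**What to change.** Reconcile the inclusion criteria, the exclusion criteria and the application instruction under Number of Subjects, in one of two ways:

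1. In exclusions 6 and 7, change fingernail to nail, so that one set of rules covers whichever nail is the target. This costs one word in each of two items and the loss of a few toenail candidates with recent sustained treatment, trauma or surgery.
2. State that the target nail must be a fingernail, and limit inclusion 3 to match. This costs one sentence and one edit. All toenail-only candidates are lost, which narrows the population and may slow recruitment.

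The first option alone still leaves the target nail undefined. Under either option, add one sentence saying how the target nail is chosen at baseline and that thickness, mNAPSI and NAPSI are all measured on it. The sponsor should decide whether the hands-only instruction fits the option chosen, and align the text accordingly.
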